2.2.2 Major Secondary Endpoint Analysis

The stratified Farrington and Manning method will be used for the stratified superiority test of major secondary endpoint #1 between 3-month and 12-month follow up for the primary analysis population of XIENCE 90 and XIENCE V USA historical control. The stratification is performed by propensity score quintiles.

To ensure all subjects to be included in this analysis, multiple imputations will be performed in calculating the propensity scores.

The exact test will be used for stent thrombosis between 3-month and 12-month follow-up against a PG for the primary analysis population as described in section 2.1.4. This test will be performed if the superiority of major secondary endpoint #1 is established.

2.2.3 Secondary Endpoint Analyses

Other secondary clinical endpoints will be descriptively analyzed for both the primary analysis population and all registered subjects without propensity stratification.

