2.1.2 Descriptive Statistics for Categorical Variables

For categorical variables such as gender, Death/MI and TLF, results will be summarized with subject counts and percentages/rates, [REDACTED] with exact two-sided 95% Clopper-Pearson⁶ confidence intervals. Differences between two comparison groups of interest, when specified, will be summarized with the difference in percentages and the Newcombe⁵ score two-sided 95% confidence interval for the difference of two percentages.

For efficacy and safety endpoint(s), relative risks (i.e., the ratio of rates), confidence interval for the relative risks, the difference in rates and the confidence interval for difference in rates (using previously-described formulas), and p-values may also be presented for hypothesis generating purposes. The p-values will be based on either Pearson's Chi-square test or Fisher's exact test by checking the expected frequency for each cell in the 2x2 contingency table against Cochran's rule⁸, i.e., if the expected frequencies for all cells are ≥ 5 , then Pearson's Chi-square test will be used, otherwise Fisher's exact test will be used.

[REDACTED]

[REDACTED]

[REDACTED]

[REDACTED]

[REDACTED]

Formulas for calculating confidence intervals for the categorical variables are given below.

1. 100(1- α) % Exact Clopper-Pearson Confidence Interval for A Single Proportion⁶

$$\text{Lower Confidence Limit} = \frac{x}{x + (n - x + 1)F_{1-\frac{\alpha}{2}}(2(n - x + 1), 2x)}$$

$$\text{Upper Confidence Limit} = \frac{(x + 1)F_{1-\frac{\alpha}{2}}(2(x + 1), 2(n - x))}{n - x + (x + 1)F_{1-\frac{\alpha}{2}}(2(x + 1), 2(n - x))}$$

where:

n = sample size

x = number of "events"

$F_{1-\frac{\alpha}{2}}(df_1, df_2)$ = the $(1 - \alpha/2)$ F - statistic for degrees of freedom df_1 and df_2

2. 100(1- α) % Newcombe Score Confidence Interval for the Difference of Two Proportions ⁷

a. 100(1- α) % Wilson Score Confidence Interval for A Single Proportion⁵

$$\text{Lower Confidence Limit} = \left(\hat{p} + Z_{\alpha/2}^2 / 2n - Z_{\alpha/2} \sqrt{(\hat{p}(1 - \hat{p}) + Z_{\alpha/2}^2 / 4n) / n} \right) / \left(1 + Z_{\alpha/2}^2 / n \right)$$

$$\text{Upper Confidence Limit} = \left(\hat{p} + Z_{\alpha/2}^2 / 2n + Z_{\alpha/2} \sqrt{(\hat{p}(1 - \hat{p}) + Z_{\alpha/2}^2 / 4n) / n} \right) / \left(1 + Z_{\alpha/2}^2 / n \right)$$

where:

$$\hat{p} = x / n$$

n = sample size

x = number of "events"

$Z_{\alpha/2}$ = 100(1- $\alpha/2$)th percentile of the standard normal distribution

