2.1.3 Propensity Score

Given that subjects in the two comparison groups (XIENCE 90 vs XIENCE V USA) are not randomized and thus may not have balanced baseline characteristics, the non-inferiority and superiority tests for 3-12 month period will be carried out through stratified analysis in the “3-month clear” population. The stratification will be performed through propensity scores (PS). For each individual a propensity score (i.e., predicted probability between 0 and 1) for group (XIENCE 90) membership will be calculated using logistics regression, with “group” as the outcome and baseline variables including demographic, lesion characteristics, and risk factors as the predictors. Subjects will be categorized into 5 groups based on the calculated propensity scores and their quintiles. Non-inferiority and superiority will then be carried out for the rate of the endpoint using the method described in sections below stratified by the propensity quintiles.

The propensity score modeling and design will be performed by an independent statistician who has no access to any outcome data of both the XIENCE 90 study and the XV USA historical control for the integrity and interpretability of study results. The independent statistician will be blinded and have no access to clinical outcome and any follow-up information to avoid introducing bias into the analysis.

[REDACTED]

[REDACTED]

[REDACTED]

[REDACTED]

[REDACTED]

Per the recent publication by Yue et al²⁸ on two-stage study designs involving propensity score adjustment, the propensity score calculation results will subsequently be sent to the FDA for review and approval prior to performing the primary endpoint and major secondary endpoint analyses.

[REDACTED]

2.1.3-1 Propensity Score Variable List

Based on prior clinical experience and clinical research, below is the list of variables that are considered to be related to assignments modeling building:

- Gender
- Age
- Creatinine
- Chronic anticoagulant
- History of stroke
- History of major bleeding
- Platelet
- Hb
- BMI
- Hypertension
- Dyslipidemia
- Prior PCI
- Prior CABG

- Prior MI
- Multivessel disease
- Clinical Presentation (ACS (NSTEMI, ACS unstable angina) vs. non-ACS)
- Diabetes
- ACC/AHA lesion complexity
- Total lesion length per patient
- RVD
- Diameter stenosis%
- Bifurcation
- Number of lesions treated
- Number of vessel treated
- Number of stents per patient
- Total stent length per patient
- Discharge P2Y12
- Paris bleeding score

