2.1.4 Hypothesis Testing

Primary endpoint analysis for 3-month DAPT

The XIENCE 90 study is powered based on primary endpoint of Death/MI between 3-month and 12-month follow-up. Death/MI is defined as the composite endpoint of all death or all myocardial infarction (Academic Research Consortium [ARC]). This primary endpoint will be evaluated between XIENCE 90 and XIENCE V USA historical control stratified by propensity score quintiles in the primary analysis population.

The stratified Farrington-Manning method will be performed to test non-inferiority (NI) of 3-month DAPT from XIENCE 90 compared to standard DAPT duration up to 12 months from

XIENCE V USA historical control. [REDACTED]

[REDACTED]

[REDACTED]

[REDACTED]

[REDACTED]

[REDACTED]

[REDACTED]

$$\hat{\delta}_i = p_{it} - p_{ic}$$

$$w_i = \frac{(N_{it} + N_{ic})}{\sum_i (N_{it} + N_{ic})}$$

$$V(\hat{\delta}_i) = \frac{p_{imt}(1-p_{imt})}{N_{it}} + \frac{p_{imc}(1-p_{imc})}{N_{ic}}$$

P_{imt} and P_{imc} are calculated as follows:

$$r_i = N_{it}/N_{ic}$$

$$a1 = - (1 + r_i + p_{ic} + r_i * p_{it} - \delta * (r_i + 2))$$

$$a2 = \delta ** 2 - \delta * (2 * p_{ic} + r_i + 1) + p_{ic} + r_i * p_{it}$$

$$a3 = p_{ic} * \delta * (1 - \delta)$$

$$u = a1**3 / (3 + 3 * r_i) ** 3 - a1 * a2 / (6 * (1 + r_i) ** 2) + a3 / (2 + 2 * r_i)$$

$$v = \text{sign}(u) * \sqrt{a1**2 / ((3 + 3 * r_i) ** 2) - a2 / (3 + 3 * r_i) }$$

$$w = 1 / 3 * (\text{arcos}(-1) + \text{arcos}(u / v ** 3))$$

$$p_{imc} = 2 * v * \cos(w) - a1 / (3 + 3 * r_i)$$

$$p_{imt} = p_{imc} + \delta$$

Major secondary endpoints analyses for 3-month DAPT

If the hypothesis testing for the primary endpoint is successful, the hypotheses testing for the major secondary endpoint #1 will be performed followed by the hypotheses test for the major secondary endpoint #2.

I. Major Secondary Endpoint #1: Bleeding rate (BARC type 2-5) from 3- to 12-month follow-up

The superiority test for the major secondary endpoint #1 will be performed stratified by propensity score quintiles in the primary analysis population.

[REDACTED]

[REDACTED]

[REDACTED]

[REDACTED]

[REDACTED]

II. Major Secondary Endpoint #2: Stent Thrombosis (ARC definite/probable) from 3- to 12-month follow-up

The exact test will be performed for major secondary endpoint #2 in the primary analysis population.

[REDACTED]

This test will be performed if the superiority of major secondary endpoint #1 is established.

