2.1.5 Survival Analyses

Survival analysis may be conducted to analyze time-to-event variables. Subjects without events will be censored at their last known event-free time point. Survival curves will be constructed using Kaplan-Meier estimates.

Summary tables for the endpoints will include failure rates (Kaplan-Meier estimates). For the primary analysis report, all available data will be used.

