2.7 Adjustments for Covariates

Unless otherwise specified, no adjustments for covariates will be made for any of the variables in the analyses.

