2.9 Sensitivity Analysis

The primary and major secondary endpoints between 3-month and 12-month follow-up will be analyzed descriptively for the 3-month clear population removing the patients who do not have antiplatelet medication compliance after 3 months.

For the 3-month DAPT arm, antiplatelet medication non-compliance beyond 3-month follow-up for 3-month clear population is defined as patients who resume P2Y12 inhibitor for more than 7 consecutive days, and/or interrupt aspirin for more than 7 consecutive days between 3-month and 12-month follow up.

[REDACTED]

[REDACTED]

[REDACTED]

[REDACTED]

[REDACTED]

[REDACTED]

[REDACTED]

In addition, a sensitivity analysis will be performed for the primary endpoint analysis to evaluate the impact of the missing outcome. The analysis will be carried out based on the primary analysis population, and by imputing the missing outcomes for each imputed baseline PS dataset, and Rubin's combination rule [29] will be used to consolidate the final analysis for the 10 duplicates of the imputed dataset. Refer to Appendix A for more details.

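### Other secondary endpoints are summarised without propensity stratification, so any contrast with the XIENCE V USA control under the visible text would be crude (low severity, cheap to improve)

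*SAP*

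**What the plan says.** SAP 2.2.3 covers every secondary endpoint outside the two major ones: "Other secondary clinical endpoints will be descriptively analyzed for both the primary analysis population and all registered subjects without propensity stratification". The list in SAP 1.3.3.2 includes all death, all MI, stroke, clinically indicated TLR and TVR, TLF, TVF and BARC 3-5 bleeding.

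The general methods allow two-group summaries of such variables. SAP 2.1.2 uses TLF as one of its examples and says: "Differences between two comparison groups of interest, when specified, will be summarized with the difference in percentages", with a Newcombe interval. For efficacy and safety endpoints it adds optional relative risks, and "p-values may also be presented for hypothesis generating purposes", from a chi-squared or Fisher test. Protocol 9.4 gives the same unstratified tests for variables such as TLR and TVR. SAP 2.7 sets the default: "Unless otherwise specified, no adjustments for covariates will be made for any of the variables in the analyses".

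The formal comparisons are handled differently. SAP 2.1.3 stratifies the non-inferiority and superiority tests because the two groups "are not randomized and thus may not have balanced baseline characteristics". Under SAP 2.1.4 the primary endpoint "will be evaluated between XIENCE 90 and XIENCE V USA historical control stratified by propensity score quintiles in the primary analysis population". SAP 2.3 keeps even descriptive subgroup comparisons with the control within quintiles, but only for the primary and major secondary endpoints.

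On time-to-event displays, Protocol 9.4 promises log-rank results without naming groups. SAP 2.1.5 says only "Survival analysis may be conducted to analyze time-to-event variables" and lists no log-rank test.

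**The concern.** The reason the SAP gives for stratifying is that the control is historical and was not randomised. That reason applies to death, MI or BARC 3-5 bleeding as much as to the composite and the BARC 2-5 endpoint. A crude difference between the studies combines the effect of DAPT duration with any difference in case mix.

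All death and all MI are the components of the primary composite, and BARC 3-5 is the stricter form of the bleeding endpoint. Readers will set them beside the adjusted results. Under SAP 2.2.3 a crude component could sit next to a stratified composite and diverge from it through case mix alone. The formal conclusions and the testing sequence do not depend on these endpoints. What is at stake is how the supporting evidence is read.

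**Working it through.** **No stated figure is at issue.** The point concerns a stated rule, so no figure in the plan has to be reproduced. The calculations below show only how large the effect could be.

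**Inputs.** Control, 3-month clear: about 1,150 (SAP 1.5). XIENCE 90: 2,000 registered (SAP 1.5), of whom 1,700 are assumed to be 3-month clear. Also assumed: no true treatment effect, a 5.0% event rate in one group, and a case-mix shift of the stated size in the other.

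**Step 1: crude interval.** Exact binomial enumeration of the Newcombe interval in SAP 2.1.2, giving the percentage of trials whose 95% interval excludes zero:

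| Rates | Shift (points) | XIENCE 90 lower | XIENCE 90 higher |
|---|---|---|---|
| 5.0 vs 5.0% | 0 | 4.9 | 4.9 |
| 5.0 vs 5.25% | 0.25 | 6.1 | 5.8 |
| 5.0 vs 5.5% | 0.5 | 9.2 | 8.6 |
| 5.0 vs 5.75% | 0.75 | 14.3 | 13.4 |
| 5.0 vs 6.0% | 1.0 | 21.4 | 20.1 |
| 5.0 vs 7.0% | 2.0 | 60.5 | 58.7 |

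Check by normal approximation at 0.75 points: SE = √(0.05×0.95/1,700 + 0.0575×0.9425/1,150) = 0.87 points. The shift is 0.75/0.866 = 0.87 SE. The chance of exceeding ±1.96 SE is then Φ(−1.09) + Φ(−2.83) ≈ 0.137 + 0.002 = 13.9%, in line with the table. The assumed 1,700 matters little: with 1,500 the 0.75-point row is 13.7 and 13.0, and with 2,000 it is 15.0 and 14.2. At 2.0 vs 2.3% the figures are 8.5 and 7.8.

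**Step 2: stratified estimate.** The estimator is Σ w_i (p_it − p_ic), with w_i = (N_it + N_ic)/Σ(N_it + N_ic) from SAP 2.1.4. The simulation uses 20,000 runs per row, a normally distributed score with the control mean shifted, log-odds of the event linear in the score, pooled quintiles and Wald intervals. The true effect is zero.

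| Control shift in score, slope | Method | Bias (points) | SE (points) | Excludes zero (%) |
|---|---|---|---|---|
| +0.3, 0.5 | crude | −0.74 | 0.87 | 12.8 |
| +0.3, 0.5 | stratified | −0.07 | 0.86 | 5.3 |
| −0.3, 0.5 | crude | 0.67 | 0.81 | 14.1 |
| −0.3, 0.5 | stratified | 0.09 | 0.83 | 5.6 |
| +0.8, 0.2 | crude | −0.74 | 0.83 | 13.6 |
| +0.8, 0.2 | stratified | −0.07 | 0.88 | 5.0 |

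**Step 3: other assumptions.** A separate calculation took 1,800 vs 1,150 subjects, control rates of 2-8%, a standardised difference in the score of 0.25-0.5 and an outcome odds ratio of 1.3-1.6 per SD. The crude difference was 0.13-1.87 points and the stratified one 0.01-0.21 points, so 88-90% of the bias was removed. A crude two-sided 5% test was falsely significant in about 6-42% of trials. The range follows directly from the assumptions.

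**Step 4: rare endpoints.** With 1,700 + 1,150 = 2,850 subjects, a 0.5% rate gives 14.25 expected events, or 2.85 per quintile. A 0.2% rate gives 5.7, or 1.14 per quintile. Stratification is of little use at that level.

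**The case against.** The strongest reply is that nothing visible commits the sponsor to this comparison. Where the SAP intends a contrast with XIENCE V USA it names the control, and SAP 2.2.3 does not. Its mention of all registered subjects fits a single-arm summary. Differences are given only when specified, and p-values are optional and labelled as hypothesis generating. The endpoints are declared descriptive and lie outside the testing sequence. Redacted lines in SAP 2.1.2 and the unseen table mock-ups may settle which contrasts appear. The control is already restricted to non-complex, high-bleeding-risk, 3-month clear subjects (SAP 1.3.1), so imbalance may be small. Every shift used above is assumed, and the simulation in Step 2 is a best case because one score captures all the confounding.

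Most of this stands, and it is why the point is rated low. It does not remove the point. The exclusion of stratification is a visible rule, not a missing detail. The score predicts membership of XIENCE 90 against XIENCE V USA, so ruling it out makes sense mainly if both studies could be shown; that is an inference, not proof. The methods text names TLF, TLR and TVR alongside unstratified two-group tools. SAP 2.3 covers other endpoints, so it does not contradict SAP 2.2.3. It does show that the sponsor does not treat descriptive status as a reason to drop the quintiles.

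**Conclusion.** The concern holds, as an optional improvement. Under the visible text, any contrast of the other secondary endpoints with XIENCE V USA would be unadjusted, between groups the SAP itself says may be unbalanced. The primary and major secondary conclusions and the alpha are untouched.

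The true size is not identifiable. Under the assumed 5.0% rate and group sizes, case-mix shifts of 0.25 to 1.0 points raise the false exclusion of zero from about 5% to between 6% and 21%. Stratification corrects only confounding that the score captures. The conclusion is conditional on a between-study contrast being shown. If none is planned, a sentence saying so closes the point.

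**What to change.** Amend SAP 2.2.3 as follows:

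- For any between-study contrast of these endpoints in the 3-month clear population, report the quintile-stratified risk difference with a 95% CI, using the weights already in SAP 2.1.4.
- Combine estimates across the imputed propensity-score datasets as in the primary analysis. The visible text does not give that pooling rule. For the missing-outcome sensitivity analysis, SAP 2.9 says that Rubin's "combination rule [29] will be used to consolidate the final analysis for the 10 duplicates of the imputed dataset".
- Show crude rates as description only, with no unadjusted between-study p-values. Stratify by quintile any between-study log-rank test shown under Protocol 9.4.
- Report all registered subjects as a XIENCE 90 single-arm summary, since the score is described only for the 3-month clear population.
- Name in advance the rare endpoints (for example hemorrhagic stroke and vascular death) for which only crude counts will be given.
- Alternatively, state that no between-study contrast of these endpoints will be made.

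A purely editorial alignment can be done at the same time: Protocol 9.4.5 refers to primary and secondary endpoints, where SAP 2.5 limits the statement to primary and major secondary ones.

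The cost is SAP wording and some programming, because each endpoint is run in every imputed dataset and combined. It needs no patients and no alpha, and loses almost no precision for common endpoints.

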2.3 Subgroups for Analysis

All of the following subgroup analyses are intended for the primary analysis population. The comparison between the XIENCE 90 study and the XIENCE V USA historical control will be analyzed descriptively within each quintile for the primary and major secondary endpoints in a specific subgroup. The above quintiles are based on the overall PS, not PS built within each subgroup, as baseline characteristics of subjects are likely to be comparable in each quintile of the overall PS.

2.3.1 Sex

Sex-specific subgroup analyses will be performed on primary analysis population for the primary endpoint and the major secondary endpoints stratified by the overall PS.

2.3.2 Diabetes

Diabetic subgroup analysis will be performed on primary analysis population for the primary and major secondary endpoints stratified by the overall PS. Analyses will be performed within the following subgroups:

- All diabetes mellitus, defined as any diabetics with or without medical treatment
- Non diabetes mellitus.

2.3.3 Covid-19 pandemic impact

In order to assess the COVID-19 impact on the primary endpoint and major secondary endpoints, a descriptive subgroup comparison will be performed on the primary analysis population between subjects whose primary endpoint follow-up overlaps with the pandemic outbreak (such as March 01, 2020 and after) and those whose primary endpoint follow-up is prior to the pandemic outbreak.

2.3.4 Other Subgroups

The following subgroups will be evaluated for the primary analysis population for the primary and major secondary endpoints stratified by the overall PS. Analyses will be performed within the following subgroups:

- Ethnicity (white versus non-white)
- Age (age \geq median vs $<$ median)
- Age \geq 65 years old (US elderly patient)
- Clinical presentation (ACS NSTEMI, ACS unstable angina, non-ACS)

2.4 Analysis Window

- 6 months
- 12 months

2.5 Handling of Missing Data

The primary and major secondary endpoint analyses will be evaluated after propensity score stratification. To handle missing data in propensity score building, multiple imputation method will be performed for baseline characteristics to compute propensity scores from these datasets.

All other analyses will be based on available data with missing data excluded. Any unused or spurious data will be noted as appropriate in the final report.

2.6 Poolability Issue

2.6.1 Multiple Geography Effect

Analysis will be performed by pooling data between geographies (US and OUS). XIENCE 90 study will enroll 2,000 subjects from approximately 100 sites globally, with at least 50% of subjects in the United States (US).

To evaluate the geography effect on the primary endpoint, Fisher's exact test will be tested for geography effect in the XIENCE 90 study against an alpha level of 0.05.

[figure not shown]
[figure not shown]
If the p-value is < 0.05 , Abbott Vascular will examine subject demographics, baseline clinical, and angiographic characteristics for possible correlations and confounding factors.

2.6.2 Multiple Center Effect

Analysis will be performed by pooling data across study sites.

The XIENCE 90 study will have 100 sites globally, with at least 50% of subjects in the United States. Subject registration is capped at 300 per site. This cap per site will prevent the scenario

where the results from a few sites dominate the overall study result. For the analysis of center effect, data from smaller sites may be combined for the analysis. Smaller sites are defined as sites with fewer than 20 subjects per site.

2.7 Adjustments for Covariates

Unless otherwise specified, no adjustments for covariates will be made for any of the variables in the analyses.

2.8 Multiplicity Issues

No multiplicity adjustment is necessary because the tests in this analysis plan are sequential.

2.9 Sensitivity Analysis

The primary and major secondary endpoints between 3-month and 12-month follow-up will be analyzed descriptively for the 3-month clear population removing the patients who do not have antiplatelet medication compliance after 3 months.

For the 3-month DAPT arm, antiplatelet medication non-compliance beyond 3-month follow-up for 3-month clear population is defined as patients who resume P2Y12 inhibitor for more than 7 consecutive days, and/or interrupt aspirin for more than 7 consecutive days between 3-month and 12-month follow up.

[REDACTED]

[REDACTED]

[REDACTED]

[REDACTED]

[REDACTED]

[REDACTED]

[REDACTED]

In addition, a sensitivity analysis will be performed for the primary endpoint analysis to evaluate the impact of the missing outcome. The analysis will be carried out based on the primary analysis population, and by imputing the missing outcomes for each imputed baseline PS dataset, and Rubin's combination rule [29] will be used to consolidate the final analysis for the 10 duplicates of the imputed dataset. Refer to Appendix A for more details.

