### 6.3.2 Antiplatelet Medications during Follow-up

- All subjects must receive  $\geq 75$  to  $\leq 100$  mg of aspirin daily throughout the study. All subjects must maintain a minimum of 75 mg of clopidogrel daily or 5 or 10 mg of prasugrel daily (10 mg preferred in most subjects\*) or 90 mg twice daily of ticagrelor for at least 3 months following the procedure.
  - The choice of P2Y12 inhibitor is per site standard of care, but clopidogrel is strongly recommended for HBR subjects.

- For subjects taking chronic anticoagulants, dual therapy (oral anticoagulant and a P2Y12 inhibitor, clopidogrel preferred) may be considered for the first 3 months after index procedure per investigator's discretion.
- At 3-month follow up, subject will be assessed for their eligibility of P2Y12 inhibitor discontinuation. Eligible subjects will discontinue P2Y12 inhibitor and receive  $\geq 75$  to  $\leq 100$  mg of aspirin daily through 1-year follow-up during the study if they are "3-month clear", defined as subjects who are free from myocardial infarction (modified ARC), repeat coronary revascularization, stroke, or stent thrombosis (ARC definite/probable) within 3 months (prior to 3-month visit but at least 90 days) after stenting AND have been compliant with 3-month dual antiplatelet therapy (DAPT) without interruption of either aspirin and/or P2Y12 receptor inhibitor for  $> 7$  consecutive days.

- Subjects who are not "3-month clear" are NOT eligible for P2Y12 inhibitor discontinuation at 3-month. These subjects will be treated per the investigator's discretion and will continue to be followed up through 12 months.

\*For prasugrel subjects  $< 60$  kg in weight or  $\geq 75$  years of age, a maintenance dose of 5 mg per day for 12 months is allowable.

The use of the above antiplatelet medications, including the start and stop date, any changes, as well as the reason to stop, will be documented in the eCRF.

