## APPENDIX IV: SCHEDULE OF EVENTS

[figure not shown]
PROCEDURE/TEST	Baseline	Pre-Procedure (within 24 hours)	Procedure	Post-Procedure	3-month ( $\pm$ 7d) Office visit 	6-month ( $\pm$ 14d) Office visit or phone contact 	12-month ( $\pm$ 28d) Office visit or phone contact 	Unscheduled visits
Subject Medical/Clinical History (Age, Sex, Risk Factors, Cardiac Status, Cardiac History)	✓							
Subject Informed Consent (Must be obtained prior to any study related testing or procedures)	✓							
General Inclusion/Exclusion Criteria	✓							
Angiographic Inclusion/Exclusion Criteria			✓					
Coronary Angiogram			✓					
Study Stent and Procedure Information			✓					
Antiplatelet Medications Loading Dose		✓	✓					
P2Y12 Inhibitor Discontinuation Eligibility Assessment					✓			
Post-procedure Antiplatelet Medications 				✓	✓	✓	✓	✓
Adverse Events			✓	✓	✓	✓	✓	✓

Subject who are “3-month clear” will discontinue P2Y12 inhibitor after 3-month visit, but continue taking aspirin through 12-month follow-up. Subjects who are not eligible for early P2Y12 inhibitor discontinuation will be treated per site standard of care.

Office visit is required for 3-month follow-up. A formal office visit is required at 3-month follow-up to ensure a thorough clinical evaluation. A telephone contact is an option only for subjects who would otherwise be lost to follow-up due to being unable to complete an office visit, but a formal follow-up visit is still preferred at 3 months.

Office visit is strongly recommended whenever possible.

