1.3 Study Design

XIENCE 90 study is a prospective, single arm, multi-center, open label trial to evaluate the safety of 3-month dual antiplatelet therapy (DAPT) in subjects at high risk of bleeding (HBR) undergoing percutaneous coronary intervention (PCI) with the approved XIENCE family of coronary drug-eluting stents.

The XIENCE family stent systems include commercially approved^a XIENCE Xpedition Everolimus Eluting Coronary Stent System (EECSS), XIENCE Alpine EECSS or XIENCE PRO^X EECSS (OUS only)^b, XIENCE PRO^A EECSS (OUS only)^c, and XIENCE Sierra EECSS,

^a The commercially approved XIENCE stent will be used in geographies where it is commercially available

^b XIENCE PRO^X is a rebrand of the XIENCE Xpedition Stent System and is only available outside of the United States.

^c XIENCE PRO^A is a rebrand of the XIENCE Alpine Stent System and is only available outside of the United States.

which are all manufactured by Abbott Vascular, Inc, Santa Clara, USA. The above XIENCE family stent systems will hereinafter be called “XIENCE” in this study.

Approximately 2,000 subjects from approximately 100 sites globally will be registered in this study, with at least 50% of subjects in the United States (US). Study population consists of non-complex HBR subjects with up to three native coronary artery lesions (a maximum of two lesions per epicardial vessel) with reference vessel diameter between 2.25 mm and 4.25 mm. Eligibility of P2Y12 receptor inhibitor discontinuation will be assessed at 3-month follow-up. Subjects who are free from myocardial infarction (modified ARC), repeat coronary revascularization, stroke, or stent thrombosis (ARC definite/probable) within 3 months (prior to 3-month visit but at least 90 days) after stenting AND have been compliant with 3-month DAPT without interruption of either aspirin and/or P2Y12 receptor inhibitor for > 7 consecutive days are considered as “3-month clear”, and will discontinue P2Y12 receptor inhibitor and continued with aspirin monotherapy after 3-month follow-up.

All registered subjects will be followed at 3, 6 and 12 months post index procedure.

The data collected from the XIENCE 90 study will be compared with the historical control of non-complex HBR subjects treated with standard DAPT duration of up to 12 months from the XIENCE V USA study, which is a US post-approval study to evaluate the safety of XIENCE V EECSS in “all-comer” population under real-world setting.

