2.2 Endpoint Analyses

2.2.1 Primary Endpoint Analysis

Primary Analysis:

A non-inferiority test will be performed on the primary endpoint for the primary analysis population of the XIENCE 90 study and the XIENCE V USA historical control stratified by propensity score quintiles [REDACTED].

To ensure all subjects to be included in this analysis, multiple imputations will be performed in calculating the propensity scores.

Secondary Analysis (as a sensitivity analysis):

In addition to the primary analysis stratified by propensity score quintile, a non-inferiority test will be performed on the primary endpoint stratified by propensity score quartile, with the same methodology as described above.

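### The descriptive compliance analysis in SAP 2.9 removes XIENCE 90 subjects for drug changes anywhere in the endpoint window, with no visible exception for changes that start after an endpoint event

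*SAP*

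**What the plan says.** SAP 2.9 states that the primary and major secondary endpoints from 3 to 12 months "will be analyzed descriptively for the 3-month clear population removing the patients who do not have antiplatelet medication compliance after 3 months". It defines non-compliance in the arm on 3-month DAPT as "patients who resume P2Y12 inhibitor for more than 7 consecutive days, and/or interrupt aspirin for more than 7 consecutive days", anywhere between the 3-month and 12-month follow-ups. That sentence is complete and does not mention the date of any endpoint event. Seven redacted lines follow it.

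SAP 1.3.2 and 1.3.3.1 count death/MI, BARC 2-5 bleeding and definite/probable stent thrombosis over the same 3-12 month period. For endpoints of this kind SAP 2.1.2 says: "For categorical variables such as gender, Death/MI and TLF, results will be summarized with subject counts and percentages/rates". On the visible text, then, the result is a simple proportion among the subjects who remain.

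Subjects who are 3-month clear "will discontinue P2Y12 receptor inhibitor and continued with aspirin monotherapy after 3-month follow-up" (SAP 1.3). Protocol Appendix IV likewise says that they "will discontinue P2Y12 inhibitor after 3-month visit, but continue taking aspirin through 12-month follow-up".

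**The concern.** The rule uses information from after the event to decide who is analysed. A subject who follows the regimen, has an MI in month 7 and then resumes P2Y12 inhibitor for more than 7 days was compliant up to the event. The rule still removes both the subject and the MI. The same happens to a stent thrombosis followed by resumption, and to a bleed followed by more than 7 days without aspirin.

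The SAP does not state what the analysis is for. A reader will naturally take it as the outcome among subjects who followed 3-month DAPT. If part of the removal is caused by the events, that rate is too favourable.

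There is a smaller gap in the definition. It names only subjects who *resume* P2Y12 inhibitor. A 3-month clear subject who never stopped has not followed the regimen as described, yet is not literally caught.

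**Working it through.** **Inputs.** The documents give no figure for this analysis to reproduce, and no visible event or removal rates. All inputs are therefore assumptions:
- *d*, deaths: 3.5%
- *m*, subjects with non-fatal MI: 1.5-2.5%, so that true death/MI is 5.0-6.0%
- *r*, share of MI subjects removed: 20-90%
- *b*, background share removed for changes unrelated to events: 0-8%

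No drug change can follow a death, so death/MI is affected only through non-fatal MI.

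**Formula A (background removal applies in full to deaths and event-free subjects; *r* is the total removal among MI subjects).**

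Rate = [d(1−b) + m(1−r)] / [d(1−b) + m(1−r) + (1−d−m)(1−b)]

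If r = b the rate is unchanged; if r > b it falls. For m = 2.0%, b = 5%, r = 50%: (0.03325 + 0.0100) / (0.04325 + 0.89775) = 4.60%, against a true 5.50%.

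- Largest shift in the range (m = 2.5%, r = 90%, b = 0): 0.0375 / 0.9775 = 3.84% against 6.00%, or −2.16 points.
- Smallest shift (m = 1.5%, r = 20%, b = 8%): 0.0442 / 0.9182 = 4.81% against 5.00%, or −0.19 points.

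**Formula B (background changes can occur only before the first event).** This is more realistic. With events spread evenly over the window, a subject with an event has about half the background chance. Here *r* is the share of remaining MI subjects removed for a change after the MI.

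Rate = [d(1−b/2) + m(1−b/2)(1−r)] / [same numerator + (1−d−m)(1−b)]

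The smallest shift becomes (0.0336 + 0.01152) / (0.04512 + 0.874) = 4.91% against 5.00%, or about −0.1 points. The largest is unchanged, because b = 0 there.

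Results at m = 2.0% (true 5.50%), with a simulation of 1,700 subjects (an assumed number) and 1,500 replicates:

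| b | r | Formula A | Formula B | Simulation |
|---|---|---|---|---|
| 5% | 20% | 5.20% | 5.25% | 5.23% |
| 5% | 50% | 4.60% | 4.66% | 4.64% |
| 5% | 80% | 3.98% | 4.06% | 4.06% |
| 8% | 20% | 5.25% | 5.33% | 5.33% |
| 8% | 50% | 4.63% | 4.73% | 4.73% |
| 8% | 80% | 4.00% | 4.13% | 4.12% |

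**Other endpoints (also assumed inputs).** For bleeding with true rate p = 6% and share *s* of bleeders removed, the rate is p(1−s) / [p(1−s) + (1−p)(1−b)]. With b = 0 to 8% this gives 4.57-4.95% for s = 25% and 3.09-3.35% for s = 50%. For stent thrombosis, where the rate is small, the share of the rate that remains is about (1−r)/(1−b): 0.50-0.54 for r = 50% and 0.20-0.22 for r = 80%.

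**Check of two possible repairs (true 5.50%).**
- *Delete only subjects whose change came before the event.* This gives 0.055(1−b/2) / [0.055(1−b/2) + 0.945(1−b)] = 5.64% at b = 5% and 5.72% at b = 8%, which is 0.14 and 0.22 points too high. Event-free subjects have the whole window in which to deviate and be deleted; subjects with events have only part of it. At b = 8%, r = 20% this error (+0.22) exceeds that of the present rule (−0.17).
- *Censor at the first pre-event change and use Kaplan-Meier.* Simulated rates are 5.49-5.52% when deviation is unrelated to risk. They are 0.04-0.07 points too low when 20% of subjects have tripled hazards of both deviation and event.

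**The case against.** The strongest objection is the redaction. The point rests on an absence, and seven redacted lines directly follow the definition. They may contain a time order, so all that can be said is that no exception is visible. This stands, and it makes the main point conditional.

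Second, nothing formal depends on this analysis. It is descriptive and sits under sensitivity analyses. A reader might infer that the non-inferiority conclusion is at risk, but the documents do not support that: "A non-inferiority test will be performed on the primary endpoint for the primary analysis population" (SAP 2.2.1), without this removal. The superiority and performance-goal tests use the same population (SAP 2.1.4 and 2.2.2).

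Third, a reader might infer that the comparison with XIENCE V USA is tilted towards the 3-month regimen. That cannot be judged, because no compliance rule for the control arm is visible.

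Fourth, the direction is not guaranteed. The illustration starts at r = 20% with b at most 8%, so cases at or below break-even are left out. Under formula A the bias vanishes at r = b. Setting formula B equal to 5.50% gives break-even at r of about 7% (b = 5%) or 11-12% (b = 8%), and below that the rate reads too high. This stands as a limit on the figures. The flaw in the rule remains, since removal can still depend on the outcome.

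On *resume*, the opening sentence of SAP 2.9 makes the intent readable. The operational definition is nevertheless narrower than that intent.

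**Conclusion.** The point holds as a minor one, conditional on the redacted lines of SAP 2.9. As visibly defined, the rule removes XIENCE 90 subjects together with events that caused their drug change, and so lowers the reported rate whenever event subjects are removed more often than others. Under the assumed inputs, a true death/MI rate of 5.0-6.0% reads about 0.1 to 2.2 points too low. Proportionally, stent thrombosis could be the most exposed. These sizes illustrate the mechanism and do not estimate what the trial will show. The formal tests are unaffected, and no conclusion is drawn about the control-arm rule or the between-group comparison. If the redacted lines already set the time order, only the wording gap on continued P2Y12 use remains.

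**What to change.** In SAP 2.9, for the XIENCE 90 arm:

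1. Replace removal of whole subjects with censoring at the first medication change of more than 7 consecutive days that starts before the subject's first event of the endpoint analysed. State that a change starting after the event does not remove the event. Report the Kaplan-Meier rate. SAP 2.1.5 already provides the framework: "Subjects without events will be censored at their last known event-free time point".
2. Do not settle for deleting only subjects with pre-event changes; that exchanges a downward error for an upward one.
3. As an analysis definition only, change *resume* to *continue or resume*, so that 3-month clear subjects who never stopped P2Y12 inhibitor count as non-compliant.

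For bleeding and stent thrombosis, cumulative incidence with death as a competing event is optional. With competing death of 2.5-4.5%, one minus Kaplan-Meier reads a 6.0% bleeding incidence as 6.08-6.14%.

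The cost is SAP wording and modest programming. The dates are already collected: antiplatelet use, "including the start and stop date, any changes, as well as the reason to stop, will be documented in the eCRF" (Protocol 6.3.2). The drawback is that censoring leaves a small bias if deviation is related to risk, 0.04-0.07 points in the scenario simulated.
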